4. STUDY POPULATION

4.1 Number of Subjects

Approximately 240 subjects will be enrolled in the study in a [REDACTED] the following treatment groups:

- Placebo of SCD-044 product [REDACTED]
- SCD-044 Tablets (Low dose)
- SCD-044 Tablets (Intermediate dose)
- SCD-044 Tablets (High dose)

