3. STUDY OVERVIEW

3.1 Study Design

Subjects in this randomized, double-blind, placebo controlled, parallel-group, multiple-center study will be assigned to treatment with the investigational products or placebo control according to a randomization scheme and [REDACTED] schedule.

- **Part I** (16 weeks): Subjects will be randomized to Placebo, Low dose ([REDACTED] mg), Intermediate dose ([REDACTED] mg) or High dose ([REDACTED] mg) of SCD-044 in 3:1:1:3 ratio

[REDACTED] to assess primary and secondary endpoints at 16 weeks.

- [REDACTED]
- [REDACTED]

Statistical Analysis Plan
Study Code SCD-044-19-16

Version Final

Date Jan 21, 2025

- [REDACTED]
- [REDACTED]
- [REDACTED]

Phone or in person contacts may be scheduled for visits [REDACTED] visits to collect information on concomitant medication, compliance with the study drug use, health changes (AEs & AESI), queries for PML and PRES and to provide instructions.

[REDACTED]

[REDACTED]

[REDACTED]

Subjects will be admitted into the study after informed consent has been obtained. An Unscheduled Visit is allowed at any time, for any reason, if in the Investigator's opinion it is warranted. If a Subject is discontinued from the study during an Unscheduled Visit, the Unscheduled Visit will be referred to as an Early Discontinuation Visit and all procedures scheduled for Early Discontinuation will be performed. If the Unscheduled Visit is not an Early Discontinuation Visit (i.e., the Subject will continue to take part in the study), then all procedures scheduled for that Unscheduled Visit will be performed. Subjects who are discontinued early from the study must attend the Follow-up visit 4 weeks after the date of Early Discontinuation.

If necessary due to the COVID-19 pandemic, Visit 18 may have assessments done at home or remote visit. Remote visits must be discussed and consulted with the CRO's and the Sponsor's medical monitor before planning. Scheduled blood collection (for these visits only) may be waived if the individual subjects have not had a clinically significant changes or undesired trend in lab or chemistry values prior to visit 15. Remote assessments or delayed visit 18 will be recorded in the source documents and noted as a minor protocol deviation.

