6. STATISTICAL METHODS OF ANALYSIS

6.1 General Principles

The statistical analyses will be performed by [REDACTED] with approval of the Sponsor, using SAS® Version 9.4 (or higher). All tables, figures and listings will be produced in landscape format.

In general, all data will be listed by subject and visit/time point where appropriate. The summary tables will be stratified by, or have columns corresponding to, treatment groups.

The total number of subjects in the treatment group (N) under the specified population will be displayed in the header of summary tables.

Data will be summarized using descriptive statistics for continuous variables. Unless otherwise specified, descriptive statistics will include number of subjects, mean, standard deviation, minimum, median, and maximum. Number of subjects with missing values will also be displayed, but only if non-zero. The minimum and maximum statistics will be presented to the same number of decimal places as the original data. The mean and median will be presented to one more decimal place than the original data. The standard deviation will be presented to two more decimal places than the original data.

In summary tables of categorical variables, counts and percentages will be displayed. The count [n] indicates the actual number of subjects in a particular category, which should always be less than or equal to the total number of subjects in the respective study group with known (non-missing) category [M]. Percentage will be obtained by: % = $n/M*100$. Unless otherwise specified, all percentages will be expressed to one decimal place.

All statistical tests will be two-sided at a significance level of $\alpha = 0.05$, unless otherwise indicated.

Baseline will be defined as the last assessment, scheduled or not, prior to the first dose of the study drug, unless otherwise specified. This notion of baseline will also be referred to as Part I baseline. Part II baseline will be defined as the last assessment, scheduled or not, prior to the first dose of the study drug in Part II. Part II baseline will be used in analysis of findings collected in Part II for subjects initially randomized to Placebo and re-randomized to SCD-044

(█ mg or █ mg) in Part II. Throughout this SAP, if the word “baseline” is used without qualification “Part I” or “Part II”, it will refer to Part I baseline.

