6.12 Safety Analyses

All safety analyses will be performed on the Safety population.

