6.12.1 Adverse Events

Adverse events will be coded using MedDRA, Version 25.0, AE coding system for purposes of summarization.

An AE will be considered as treatment-emergent (TEAE) if the date of onset is on or after the date of the first study drug administration. AEs with unknown start dates will be counted as treatment-emergent unless the AE resolution date is prior to the study drug start date. If the start date is partially missing, the AE will be considered treatment-emergent, unless the month and year (when available) rule out the possibility that the event occurred post start of study drug dosing.

A TEAE is defined as treatment-related if its relationship to study medication is recorded as “Possible”, “Probable” or “Definite” on the eCRF. In case the relatedness was not assessed, the most conservative result (related) will be chosen for the analysis.

Cardiovascular AEs will be defined as AEs with MedDRA system organ class “Cardiac disorders” or “Vascular disorders”.

Adverse events that are of special interest, that represent signs/symptoms of Progressive Multifocal Leukoencephalopathy (PML) or of Posterior Reversible Encephalopathy Syndrome (PRES) and that are cardiac arrhythmias will be marked on the eCRF.

Events will be assigned to Part I or Part II of the study based on the date of onset, i.e. AEs that start prior to the first dose of the Part II treatment will be assigned to Part I and AEs that start on or after the date of the first Part II dose will be assigned to Part II.

In summaries of TEAEs a subject experiencing the same AE multiple times on the same treatment will only be counted once for that preferred term and treatment. Similarly, if a subject experiences multiple AEs within the same system organ class on the same treatment that subject will be counted only once in that system organ class and treatment. When summarizing AEs by severity, only the most severe occurrence within the preferred term or system organ class and treatment will be used. Similarly, when summarizing AEs by relationship to study drug, only the most related occurrence within the preferred term or system organ class and treatment will be selected for displays in summary tables.

All AE summaries will be presented in 3 ways:

1. For events in Part I only, using Part I treatment groups, with the additional groups SCD-044 Any Dose (including the three SCD-044 groups) and Total (including all subjects).

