2. For events in Part II only, using Part II treatment groups, with the additional group Total.
3. For the entire study only for subjects initially randomized to SCD-044 and thus staying on the same treatment throughout the study, using the three active treatment groups with the additional group Total.

An overall summary for the Safety population will include, by treatment and overall, the number and percentage of subjects reporting at least 1 TEAE in the following categories:

- Any TEAE
- Treatment-related TEAE
- Serious TEAE
- Serious drug-related TEAE
- TEAE leading to discontinuation of the study medication
- Treatment-related TEAE leading to discontinuation of the study medication
- TEAE requiring temporary interruption of the study medication
- Treatment-related TEAE requiring temporary interruption of the study medication
- TEAE leading to death.
- TEAEs of special interest

Additional overall summary of cardiovascular TEAEs will include, by treatment and overall, the number and percentage of subjects reporting at least one cardiovascular TEAE in the following categories:

- Any cardiovascular TEAE
- Treatment-related cardiovascular TEAE
- Serious cardiovascular TEAE
- Cardiovascular TEAE leading to discontinuation of the study medication
- Cardiovascular TEAE leading to death.
- Cardiovascular TEAEs of special interest
- Cardiac arrhythmias

The following TEAE frequency tables will be prepared summarizing the number and percentage of subjects reporting at least one TEAE by MedDRA System Organ Class (SOC) and preferred term PT, by treatment group for the Safety population:

- All TEAEs
- Serious TEAEs
- Treatment-related TEAEs
- Serious treatment-related TEAEs
- TEAEs leading to discontinuation of the study medication
- Treatment-related TEAEs leading to discontinuation of the study medication
- TEAE requiring temporary interruption of the study medication
- Treatment-related TEAE requiring temporary interruption of the study medication
- TEAEs occurring in $\geq 2\%$ in any treatment group
- TEAEs of special interest
- Cardiac arrhythmias
- TEAEs with onset during the [REDACTED] period in Part I and in Part II
- TEAEs by Severity
- TEAEs by Relationship to Study Drug.

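### No adverse event table in SAP 6.12.1 pools all SCD-044 subjects from first active dose, and the by-actual-dose summary promised in protocol 9.7 is missing

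*SAP*

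**What the plan says.** SAP 6.12.1 introduces its layouts with "All AE summaries will be presented in 3 ways":

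1. **Part I events**, by Part I group, "with the additional groups SCD-044 Any Dose (including the three SCD-044 groups) and Total (including all subjects").
2. **Part II events**: "For events in Part II only, using Part II treatment groups, with the additional group Total".
3. **Whole study**: "For the entire study only for subjects initially randomized to SCD-044 and thus staying on the same treatment throughout the study".

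The same section adds tables for the early dosing period. In Part II these carry the two Placebo/SCD-044 groups and a Total of those two.

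SAP 6.1.1 lists five Part II groups, defined by Part I and Part II treatment together: two Placebo/SCD-044 groups and three continuing SCD-044 groups. SAP 6.1 defines a separate Part II baseline "for subjects initially randomized to Placebo and re-randomized to SCD-044".

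On the analysis set, SAP 6.12 says "All safety analyses will be performed on the Safety population".

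Protocol 9.7 says AEs will, in addition, be tabulated by the dose the subject was actually taking at onset, to allow for dose reductions. SAP 6.12.1 has no such table. SAP section 8 says only the handling of intercurrent events was expanded and nothing else departs from the protocol.

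**The concern.** Safety and tolerability is a stated objective of this dose-ranging study. For uncommon events, such as events of special interest and arrhythmias, the useful quantity is how many subjects had the event after first taking SCD-044, out of all who took it. The trial produces that information for the originally randomised SCD-044 subjects and again for the placebo subjects who switch, but no planned table brings the two together.

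The one column where switchers and other SCD-044 subjects meet is the Part II Total. There, people in their first weeks on drug are combined with people who have already tolerated 16 weeks. That column estimates neither the rate on starting treatment nor the rate on continuing it.

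The SAP restarts the clock at the switch elsewhere: for change from baseline (6.9.2.1), laboratory values (6.12.2) and time to response (6.9.2.4). For AEs it does not carry this into a pooled estimate. AE listings also count onset days from first study drug, which for switchers is placebo.

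**Working it through.** **Inputs**

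- Planned size: "Approximately 240 subjects will be enrolled in the study" (Protocol 4.1).
- Allocation, placebo : low : intermediate : high: "of SCD-044 in 3:1:1:3 ratio" (SAP 3.1).
- Placebo subjects who enter Part II go to one of two SCD-044 doses. SAP 6.1.1 lists no group that stays on placebo.
- Part I dropout in the placebo arm, *d*: not given. Assumed 0 to 30%.
- Split of switchers between the two doses: not visible. Assumed even, for step 3 only.

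The plan states no number of switchers, so there is no figure to reproduce.

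**Step 1. Arm sizes.** Placebo 240 × 3/8 = 90; low 240 × 1/8 = 30; intermediate 30; high 90. Randomised to SCD-044: 30 + 30 + 90 = 150. This is the most that the Part I pooled active column and the whole-study Total can hold.

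**Step 2. All doses pooled from first active dose.** Switchers = 90 × (1 − d). Pooled n = 150 + 90 × (1 − d). One-sided 95% upper bound with zero events = 1 − 0.05^(1/n). Chance of at least one case of a 1% event = 1 − 0.99^n.

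| d | Switchers | Pooled n | Switchers' share | Upper bound | Chance of seeing a 1% event |
|---|---|---|---|---|---|
| as planned, no pooling | – | 150 | – | 2.0% | 77.9% |
| 0% | 90 | 240 | 37.5% | 1.2% | 91.0% |
| 10% | 81 | 231 | 35.1% | 1.3% | 90.2% |
| 20% | 72 | 222 | 32.4% | 1.3% | 89.3% |
| 30% | 63 | 213 | 29.6% | 1.4% | 88.2% |

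**Step 3. A single dose.** Switchers go to two doses and only one active dose has 90 subjects. If the two doses differ, at least one is a 30-subject dose. With an even split that dose gains 63/2 = 31.5 to 90/2 = 45 subjects, so first exposures rise from 30 to about 61.5 to 75. The bound falls from 1 − 0.05^(1/30) = 9.5% to between 1 − 0.05^(1/61.5) = 4.8% and 1 − 0.05^(1/75) = 3.9%.

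**Step 4. Where a switcher's first 16 weeks on SCD-044 appear.**

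| Planned table | Included? |
|---|---|
| Part I, pooled active column | No |
| Part II, own Placebo/SCD-044 column | Yes, alone |
| Part II, Total | Yes, mixed with continuing subjects |
| Early-period table, Part II | Yes, switchers only |
| Whole study | No |

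**Step 5. Protocol against SAP.** A table by actual dose at onset would put switchers and originally randomised subjects at the same dose together. It would fill the gap only in part, because it is not limited to first exposure. Its absence from SAP 6.12.1 does not fit with section 8.

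**The case against.** **Switchers are already reported.** They have two columns of their own, are in the Part II Total, and have early-period columns and listings. A reader might infer that their AEs are lost from the safety report; the documents do not support that. For one dose, the Part I column and the Placebo/SCD-044 column contain different people, so counts and denominators can largely be added by hand. This stands, and it limits the point to a missing summary. The windows do not match exactly, though: Part I ends at Week 16, while Part II events run to the follow-up visit at Week 36, which is 20 weeks. A hand-added figure is therefore not a clean first-16-weeks rate.

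**Separate reporting is defensible.** Switchers stayed through 16 weeks of placebo and start later, so pooling mixes a selected cohort with subjects randomised at baseline. This also stands. It is why the added columns should be descriptive and should not replace the Part I comparison.

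**Part II denominators.** Because all safety analyses use the Safety population and no Part II set is named, a reader might infer that subjects who left in Part I stay in the Part II denominators and dilute the rates for continuing arms. The text points the other way. SAP 6.1.1 defines Part II groups by treatment in both parts, so someone who never entered Part II belongs to none of them, and SAP 6.1 counts N within the treatment group. The continuing arms carry the same labels in both parts and the table shells are a separate document, so one clarifying sentence is worth having. Dilution is not a stated feature of the plan.

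**Conclusion.** The point holds as a gap in presentation plus a mismatch between protocol and SAP. It is not an error that biases a planned comparison. The mismatch is directly documented and rests on no assumption.

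The size of the gap rests on the planned 240, on every placebo subject who completes Part I being switched, and on an assumed 0 to 30% Part I dropout. On that basis 63 to 90 first exposures, about 30% to 37.5% of all those the trial would generate, sit outside every pooled first-exposure estimate. A reader might take the number as close to the full 90. The documents give no dropout rate, so only the range can be stated. The dose-level figures also need the assumed even split.

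This is a cheap improvement that should be made. It matters mainly for uncommon events and for the smaller dose groups.

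**What to change.** In SAP 6.12.1:

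- **(a)** Add descriptive tables from first active dose, by dose and for any SCD-044 dose. Pool subjects randomised to SCD-044 with switchers, each counted from their own first SCD-044 dose. Give one set for the first 16 weeks on SCD-044 and one for all SCD-044 exposure, with events per 100 patient-years. Cover at least all treatment-emergent AEs, serious ones, events of special interest and cardiac arrhythmias.
- **(b)** Split the Part II Total into newly started and continuing subjects.
- **(c)** Restore the summary by actual dose at onset from protocol 9.7, or list its removal in SAP section 8.
- **(d)** State in one line that Part II denominators are Safety population subjects with at least one Part II dose, as SAP 6.1.1 already implies.

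Keep all comparisons with placebo in Part I. Footnote the pooled tables to say that switchers start later and are selected by having completed Part I, so the columns are descriptive only.

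The cost is some SAP wording and a few more tables. No new data, visits or subjects are needed.

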6.12.2 Laboratory tests

A central laboratory will be used for all assessments unless noted otherwise. Unscheduled laboratory assessments can be performed at discretion of the Investigator in response to AEs. The laboratory assessments include:

Hematology: at all on-site study visits a blood sample will be collected for total and differential WBC count, Absolute Neutrophil count (ANC), ALC, Platelet count, Hemoglobin, Hematocrit, Mean Corpuscular Volume (MCV) testing. Additionally, total WBC count with differential counts including ALC and ANC counts will be performed pre-dose and at 1h, 2h, 4h and 6h post-dose on Day 29 (Week 4).

Lipid profile: at the study visits 1, 2, 10 and 17 (Screening and study weeks 0, 16, and 32) a blood sample will be collected for LDL, HDL and total cholesterol and Triglycerides testing.

Clinical chemistry: at the study visits 1, 2, 7, 8, 10, 15, 16, and 17 (Screening and study weeks 0, 4, 8, 16, 20, 28, and 32) a blood sample will be collected for sodium, potassium, chloride, calcium, magnesium, bicarbonate, phosphate, blood urea nitrogen, random glucose, albumin, total protein, alkaline phosphatase, creatinine, ALT, AST, gamma glutamyl transferase (GGT), total bilirubin, conjugated bilirubin testing.

Coagulation profile: at the study visits 1, 2, 10, and 17 (Screening and study weeks 0, 4, 16, and 32) a blood sample will be collected for PT, INR, and aPTT testing.

Serology: at Screening visit a blood sample will be collected for: anti-VZV IgG, HIV antibodies, HBsAg, and HCV antibodies testing.

QuantiFERON Gold test: at Screening Visit a blood sample will be collected for TB antigens testing. A maximum of 2 QuantiFERON tests are allowed. A retest is permitted if the first is indeterminate; the result of the second test will be used. Chest X-ray should be performed for subjects with a positive or 2 successive indeterminate QuantiFERON test results; a chest X-ray is acceptable if performed within the past 3 months and available at a site along with an associated report.

Serum pregnancy test: at Screening Visit a blood sample will be collected for serum beta-hCG testing.

The following tests will be performed at a clinic site:

Urinalysis dipstick: at the study visits 1, 2, 10, and 17 (Screening and study weeks 0, 16, and 32) a urine sample will be collected for pH, specific gravity, protein, glucose, ketones, and blood testing.

Microscopic exam may be performed at the local or central laboratory at the discretion of the Investigator if the dipstick is positive (i.e., trace or above).

Urine Pregnancy Test: at the study visits 2, 7, 8, 9, 10, 15, 16, 17, 18 (study weeks 0, 4, 8, 12, 16, 20, 28, 32, and 36) a urine sample will be collected in women of childbearing potential for hCG testing.

A positive result should be confirmed by a serum beta-hCG test. A confirmed positive urine pregnancy test during the treatment periods of the study requires immediate interruption of study drugs and the subject must be discontinued from the study.

Labs need not be repeated at baseline if these assessments for screening visit are performed within 2 weeks prior to the Visit 2.

For Hematology, Chemistry, and Coagulation profile the labs, which were abnormal and clinically significant at EOT, need to be repeated at safety follow-up visit.

[figure not shown]
Hematology, chemistry (including lipid profile), coagulation and continuous urinalysis parameters and their changes from baseline will be summarized descriptively by visit and treatment group. For WBC and differentials (absolute counts and percentages) percent change from baseline will also be summarized.

Additionally, hematology (WBC and differentials) results obtained during Day 29 (Week 4) visit will be summarized by timepoint with changes and percent changes from baseline.

Shifts from baseline among the categories Normal (within the reference range), Low (below the reference range) and High (above the reference range) will be presented by visit.

In the analyses of change from baseline and shifts from baseline above, Part II baseline will be used for the groups Placebo/SCD-044 [REDACTED] mg and Placebo/SCD-044 [REDACTED] mg, while Part I baseline will be used for the other treatment groups.

All results will be listed.

6.12.5 Physical Examination

The investigator, sub-investigator or appropriately delegated designee will perform a physical examination, prior to the Subject starting study drug and at the end of treatment. Physical examinations may also be done at the discretion of the investigator. The physical examination will include, at a minimum, examination of the Subject's general appearance, comprehensive skin examination, HEENT (head, eyes, ears, nose and throat), heart, lungs, musculoskeletal system, neurological system, lymph nodes, abdomen and extremities.

Each body system will be classified as normal, abnormal not clinically significant or abnormal clinically significant.

Number and percentage of subjects with normal, abnormal not clinically significant or abnormal clinically significant findings will be presented by body system, visit and treatment group.

All results will be listed.

6.12.6 Prior and Concomitant Medication

Prior and concomitant medication will be coded according to the World Health Organization – Drug Dictionary version MAR 01, 2022 and the Anatomical Therapeutic Chemical (ATC) classification system. Prior medications are defined as those taken within 30 days before the first dose of the study drug (i.e., start and end date before the first dose of the study drug). Concomitant medications are defined as those taken at the time on or after the first dose of the study drug. Any medications that were started before the first dose of the study drug and continued after dosing will be considered a concomitant medication.

Medications concomitant with Part I will be defined as those taken at any time on or after the first study drug dose date in Part I and prior to the first study drug dose date in Part II. Medications concomitant with Part II will be defined as those taken at any time on or after the first study drug dose in Part II.

All previous and concomitant medication will be listed by subject. Concomitant medications in Part I, in Part II and in the study overall will be summarized by treatment group, ATC class (highest level available) and preferred name. The summary for the study overall will include only subjects initially randomized to SCD-044 and thus staying on the same treatment throughout the study. This analysis will be done for the Safety population.

All prior and concomitant medications will be listed.

